9.2 Allocation concealment

The allocation sequence will be hosted by the Sheffield CTRU in accordance with their standard operating procedures and will be held on a secure server. Access to the allocation sequence will be restricted to those with authorisation. The sequence will be concealed until recruitment, data collection, and analyses are complete.

9.3 Implementation

The allocation sequence will be created by a Sheffield CTRU statistician who is not otherwise associated with the trial. At the consent visit, a health professional who is named on the delegation log, will go over the patient information sheet again with the study candidate and answer any questions. If the PWCF is still willing to enter the trial, they obtain full written consent and complete the eligibility form. If the participant is eligible, then baseline assessments will be taken. The recruiting health professional will log into the remote, secure Internet-based randomisation system and enter basic demographic information, after which the allocation will be revealed.

9.4 Blinding

After revelation of the allocation, only the statisticians will be blinded to allocation as per CTRU SOPs (ST001 and ST005).

10. Data collection, management and analysis

10.1 Quantitative data

10.1.1 Data collection methods

Data handling and record keeping. The Sheffield CTRU will oversee data collection, management and analysis and ensure the trial is undertaken according to Good Clinical Practice Guidelines and CTRU standard operating procedures. Data will be collected and retained in accordance with the Data Protection Act 1998. Patients will be reassured that all data which are collected during the course of the research will be kept strictly confidential.

The study team will train those collecting data in the study procedures before the trial begins. Data will either be collected directly from the participants, carers, interventionist, CFHealthHub or from source documents (e.g. patient notes) and input onto the CRF or Sheffield CTRU's electronic web-based data capture system (Prospect). The Data Monitoring and Management Plan for the study will provide further guidance on the types and levels of data and how these will be monitored and verified. Some essential documents may be posted to the central team to facilitate this e.g. participant consent forms in which case this will be detailed in the appropriate participant PIS and consent forms.

© 2018 Sheffield Teaching Hospitals NHS Foundation Trust. All rights reserved.

The CTRU will perform checks on the data to ensure data is being captured and alert the local interventionist if there is an indication of a prescription change and a need to check pseudomonas (or other microorganism) status. This is required for the correct denominator to assess "normative adherence". Data will be extracted from the CF registry to understand exacerbations in the preceding 12 months since prior exacerbations can have a bearing on the optimum target regimen.

Plans to promote participant retention and complete follow-up.

Participant retention will be ensured by the following procedure:

- 1. At each point of contact, the interventionist will check with the participant that the Qualcomm hub or Smartphone hub is plugged in and turned on. A member of CTRU who is performing data and prescription checks may alert the interventionist. They will remind the participant of the proximity required for data transfer (10 metres)
- 2. In the event of no data being displayed in CFHealthHub for the first two weeks of trial participation, (and the participant is not known to be on holiday) the interventionist will make contact with the participant (Email/Text/Telephone call) and follow the troubleshooting procedure (see section below)

Troubleshooting:

Data capture will be monitored both by interventionist at the site and centrally by the CTRU. In the event of data not being uploaded patients will be contacted to trouble shoot problems. Troubleshooting includes (but it not limited to) checking:

- That the Qualcomm hub is plugged in
- That the Qualcomm hub is working (showing solid green and yellow lights on the display)
- That they have been within range of the Qualcomm hub sufficient to facilitate data transfer (10 metres)
- The interventionist may perform a home visit to run a test nebulisation with the participant and inform CTRU of the date this occurred. This will help assist with technical issues in patients in this group.

Patients will be offered support to suit their circumstances including home visits (conducted by the members of the site research team) where necessary. Documentation for assisting participants with troubleshooting issues will be incorporated in the CFHealthHub manual. Troubleshooting will be conducted extensively in the first 2 weeks from participant entry into the study (consent visit) for both control and intervention arm participants. Beyond this point:

- 1. there will be a 6-month data check for control arm participants performed by CTRU. CTRU will follow up with local interventionist's, cases where data has not been coming through to CFHealthHub and facilitate troubleshooting
- 2. intervention arm participants will have ongoing data checks throughout the trial period
- 3. both control and intervention arm participants will be asked to complete a manual data transfer at the 12 month research visit

10.1.2 Data Management

Anonymised trial data will be entered onto a validated database system designed to an agreed specification between the Chief Investigator and Sheffield CTRU. The research staff at sites (mainly the ACtiF interventionist) will be responsible for data entry locally. The Sheffield CTRU Trial Manager, research assistant and the Data Management Team will work with sites to ensure the quality of data provided. The study manager, research assistant, data manager, PI's, any research nurses and site interventionist will have

© 2018 Sheffield Teaching Hospitals NHS Foundation Trust. All rights reserved.

access to the anonymised data on the database through the use of usernames and encrypted passwords. The system has a full electronic audit trail and will be regularly backed up. The secure data management system will incorporate quality control procedures to validate the study data. Error reports will be generated where data clarification is needed. Output for analysis will be generated in a format and at intervals to be agreed between Sheffield CTRU and the Chief Investigator.

Trial documents will be retained in a secure location during and after the trial has finished. The study will use the CTRU's in-house data management system (Prospect) for the capture and storage of participant data. Prospect stores all data in a PostgreSQL database on virtual servers hosted by Corporate Information and Computing Services (CiCS) at the University of Sheffield. Prospect uses industry standard techniques to provide security, including password authentication and encryption using SSL/TLS. Access to Prospect is controlled by usernames and encrypted passwords, and a comprehensive privilege management feature can be used to ensure that users have access to only the minimum amount of data required to complete their tasks. This can be used to restrict access to personal identifiable data.

Participants who give consent to the qualitative part of this study will also give consent to their name and address to be given to the University of Sheffield qualitative research staff in order to be contactable.

10.1.3 Data quality assurance

Prospect provides a full electronic audit trail, as well as validation and verification features which will be used to monitor study data quality, in line with CTRU SOPs and the Data Management Plan (DMP). Error reports will be generated where data clarification is required. Rates of missing data and data points which are out of the expected or allowed range will be presented to the team at monthly management group meetings.

10.2 Qualitative data

10.2.1 Audio recordings of consultations

All intervention visits at each centre will be audio recorded with permission from the patient from which a sample will be selected to assess the fidelity of implementation of the intervention and mechanisms of action throughout the trial. A purposive sample will be selected for analysis to ensure assessment at site and interventionist level and during early, mid and late phases of recruitment into the RCT. Encrypted digital recorders will be used at each site and recordings sent securely to the research team for analysis.

10.2.2 Semi-structured interviews: PWCF

From 3-6 centres we will interview a total of 16-20 PWCF. Initial approach will be made via email or post where the information sheet, consent form and invitation letter is sent to the participant. Following this, the qualitative researchers will email/phone or text the participant to discuss the study and if the participant is happy will arrange a suitable time (based on the participants preference) to seek informed consent and conduct the interview. We will interview 8-10 of them around 2-3 months of starting the intervention to gain feedback on changes made since the pilot trial, and 8-10 of them around 6-12 months into the intervention to seek longer term views of the intervention. This will build on the qualitative research in the feasibility study where PWCF were interviewed around 1 month and then 3-6 months into the intervention process. We will sample based on baseline adherence levels and maximum variation of socio-demographic characteristics.

10.2.3 Semi-structured interviews: interventionists

We will interview the interventionist in each centre (n=20). The interventionists may have different lengths of experience of working with CF, nebulisers, or behaviour change and we will consider the influence of differences in backgrounds on their ability to implement the intervention. The interventionists will work in different centres and we will consider how context has affected implementation and feasibility. Interviews will take place between 3 and 8 months into the RCT.

10.2.4 Semi-structured interviews: PIs

We will interview the PI in some centres (n=6) where there are specific issues identified during the trial to understand how the context of different centres may be affecting implementation and feasibility of the RCT and the intervention. Interviews will take place between 3 and 12 months into the RCT.

10.2.5 Undertaking the interviews

We will use an encrypted digital recorder. Reflexive notes will be made during and after the interviews. We expect interviews to last around one hour.

11. Data analysis

11.1 Quantitative analysis

The analysis will be performed after data lock by a CTRU statistician under the supervision of the senior study statistician. As the trial is a pragmatic parallel group RCT data will be reported and presented according to the CONSORT 2010 statement [55]

Clinical outcome measures will be summarised overall and by randomized group. Baseline demographic (age, gender), physical measurements (e.g. weight, height, BMI), and patient reported outcome measures (EQ-5D-5L, PAM-13, Assessment of Routine, MAD-3, SRBAI, CFQ-R, GAD-7, COM-BMQ, PHQ-8), and clinical measurements (e.g. FEV1, IV days in last registry year) will be described and summarised overall and for both treatment groups. We will report rates of consent, recruitment and follow-up by centre and by randomised group.

The primary outcome is the number of pulmonary exacerbations treated with IV antibiotics over the 12 month post-consent follow-up period.

Secondary continuous outcomes such as 12-month post consent FEV1, BMI EQ-5D-5L, PAM-13, Assessment of Routine, MAD-3, SRBAI, CFQ-R, GAD-7, COM-BMQ, PHQ-8) will be analysed with a multiple linear regression model with the baseline value of the outcome and randomised group as covariates. The treatment group coefficient and its associated 95% confidence interval will be reported from the various multiple linear regression models. The mean level of adherence (to prescribed medication) between the CFHealthHub and control groups over the 12 month post-consent follow-up period will also be reported and compared between the groups and a 95% confidence interval (CI) for the mean difference in this parameter between the randomised groups will also be calculated.

Further analyses with the objective nebuliser data will be performed to explore the process of habit formation with the delivery of the adherence intervention. The analyses will include:

- (a) generating objective habit scores by taking into account time of nebuliser use
- (b) using statistical process control to identify when periods of stability is achieved
- (c) other time-series methods, including cross-correlation between habit scores and adherence.

Adverse events will be based on serious adverse events (SAE) case report forms. A serious adverse event is defined as any adverse event or adverse reaction that results in death, is life-threatening, requires hospitalisation or prolongation of existing hospitalisation, results in persistent or significant disability or incapacity, or is a congenital anomaly or birth defect. The following summaries will be presented as overall rates and stratified by AE classification:

[figure not shown]
- the number and percentages of patients reported as having Serious Adverse Events (SAE) in each treatment group; and,
- the number and percentages recorded as having all forms of Adverse Events (AE) in each group.

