Therefore assuming a mean difference of 0.5 PE over a 1 year follow-up between the intervention and control groups is the target difference we wish to detect; a SD of 1.5; 90% power and two-sided significance level of 5%; a design effect of 1.16 to allow for any clustering of outcomes by physiotherapist (ICC of 0.01 and cluster size of 17) then we require 222 subjects per arm (444 in total) to detect this difference. If we assume a 20% loss to follow-up by 12 months then we would need to recruit 556 patients (278 per arm). Meta-analysis level evidence indicates that date and time stamped data improves adherence. Patients recruited to the active limb of the trial will receive feedback of time and dated stamped adherence data which the meta-analysis evidence suggest will be beneficial. We have been provided with sufficient funded chipped nebulisers to allow us to recruit up to 35 patients in each centre which may allow us to exceed our study targets based on our power calculations. We consider that it is in patients best interests to recruit them if the opportunity arises since the evidence suggests this will benefit their adherence and RCT evidence supports that the treatments prescribed are beneficial. In addition power calculations are an inexact since so increasing

our power will reduce the chance of a false negative trial result. Thus since over recruitment is associated with patient benefit we think that if the opportunity arises we should do this.

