9.1 Sequence generation

Participants will be allocated in equal proportions to one of the two groups using a computer generated pseudo-random list, stratified by centre and the number of days participants have been on IV antibiotics in the previous 12 month period as collected at consent visit, with random permuted blocks of varying sizes. The two categories for stratification within the number of IV days will be (i) less than or equal to 14 days and (ii) greater than 14 days.

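### The model fixed in Protocol 11.1 for continuous secondary outcomes omits the stratification factors and the interventionist clustering that the design allowed for

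*Protocol*

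**What the plan says.** Protocol 11.1 gives one model for the continuous secondary outcomes (FEV1, BMI and the questionnaire scores). They "will be analysed with a multiple linear regression model with the baseline value of the outcome and randomised group as covariates". The inference comes straight from that fit: "The treatment group coefficient and its associated 95% confidence interval will be reported from the various multiple linear regression models". The section does not defer this model to the SAP.

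Two other sections describe a design with more structure. Protocol 9.1 allocates participants individually in a 1:1 ratio, "stratified by centre and the number of days participants have been on IV antibiotics in the previous 12 month period", with the IV-day factor split at 14 days. Protocol 8.1.2 inflates the sample size by "a design effect of 1.16 to allow for any clustering of outcomes by physiotherapist (ICC of 0.01 and cluster size of 17"). That allowance is made for the primary outcome, pulmonary exacerbations.

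Three further facts bear on the point. Protocol 10.2.3 plans to interview the interventionist in each centre, 20 in all, which implies about one per centre. Protocol 6.5 says that controls do not receive the structured intervention. Protocol 6.4.4.6 has the interventionist collect 12-month outcome data from all participants, in both arms.

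**The concern.** A model normally carries the features used to design the trial. This one carries neither.

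- **Stratification factors.** Stratified allocation balances centre and IV-day group between arms, so the treatment contrast is largely free of the variation they cause. A regression that omits them leaves that variation in its residual. Its standard error is then too large, and the precision that stratification was meant to buy is lost.
- **Interventionist clustering.** Participants treated by the same interventionist may share an effect that controls do not share. A model that treats all participants as independent gives a standard error that is too small.

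At stake is whether the intervals for the secondary outcomes have the right width. The point estimates are little affected.

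**Working it through.** **1. The plan's own figure.** Inputs from Protocol 8.1.2: difference 0.5, SD 1.5, 90% power, two-sided 5%, ICC 0.01, cluster size 17, 20% loss.
- Design effect: 1 + (17 − 1) × 0.01 = 1.16.
- The t-based size without clustering is 191 per arm; 191 × 1.16 = 221.6, rounded up to 222. (The normal approximation gives 190, and 190 × 1.16 = 220.4, so 221.)
- 222 / 0.80 = 277.5, so 278 per arm and 556 in total.

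The stated size reproduces. The clustering allowance accounts for 222 − 191 = 31 evaluable participants per arm.

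**2. Clustering ignored, intervention arm only.** The protocol gives no ICC for any secondary outcome, so carrying over 0.01 and 17 is an assumption.
- Variance inflation of the contrast: (1.16 + 1) / 2 = 1.08.
- Standard-error ratio: √1.08 = 1.039. The correct SE is 3.9% larger than the reported one.
- True two-sided error: 2 × [1 − Φ(1.96 / 1.039)] = 5.9%, so coverage is 94.1%.

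The cluster size matters. With 222 evaluable per arm, 17 per cluster implies 222 / 17 ≈ 13 clusters. With 20 centres it is 222 / 20 ≈ 11 per cluster: design effect 1.10, inflation (1.10 + 1) / 2 = 1.05, SE ratio √1.05 = 1.025, error 5.6%.

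**3. Stratification factors ignored.** Let R² be the share of residual variance, after the baseline value, that centre and IV-day stratum explain. The protocol gives no figure; 5% to 10% is assumed.
- Interval widening: 1/√0.95 = 1.026 to 1/√0.90 = 1.054.

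**4. Both together.** The ratio of true to reported SE is approximately √[1.08 × (1 − R²)].
- R² = 5%: √1.026 = 1.013, coverage about 94.7%.
- R² = 10%: √0.972 = 0.986, coverage about 95.3%.
- The two cancel at R² = 1 − 1/1.08 = 7.4%.

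**5. Simulation.** 3,000 runs per scenario (about ±0.8 points), both arms in every centre, allocation balanced on centre and IV stratum, baseline correlation 0.5. All effect sizes other than the ICC of 0.01 are assumed.

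| Scenario | Stated model | Plus centre and IV stratum, no therapist term |
|---|---|---|
| Therapist ICC 0.01; no centre or stratum effect; 20 × 11 per arm | 93.9% | 93.9% |
| Same; 13 × 17 per arm | 94.0% | 94.0% |
| Therapist ICC 0.01; centre ICC 0.01 to 0.10; stratum effect 0 to 0.6 SD; 20 × 11 per arm | 95.1% to 96.3% | 93.9% to 94.8% |
| Therapist ICC 0.05; no centre or stratum effect; 20 × 11 per arm | 91.3% | 91.1% |

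The third row shows the offset. It also shows that adding only the stratification factors removes the conservatism and leaves the clustering uncorrected.

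**The case against.** The strongest case against the point is that no miscalibration is demonstrated. The two omissions pull in opposite directions and, at the protocol's own ICC, are of similar size. Where centre or stratum effects were present with that ICC, the stated model's coverage was nominal or slightly conservative. The ICC of 0.01 is a planning allowance for exacerbations and does not show that FEV1 or a questionnaire score clusters. Adjustment for the baseline value may already absorb much of what centre and IV days would explain. Only secondary outcomes are touched, and Appendix 1 names no key secondary outcome.

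Most of this stands, and it rules out three stronger readings that a reader might infer.

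- **That the intervals lack their stated coverage.** The documents contain no ICC or variance share for these outcomes from which that could be shown.
- **That the full 1.16 applies to the contrast, giving 6.9% error.** This needs independent therapist effects in both arms. Controls do not receive the intervention (Protocol 6.5), and randomisation is within centre, so an effect common to both arms, such as one interventionist measuring everyone, largely cancels from the comparison.
- **That the primary analysis has the same fault.** Protocol 11.1 states no primary model, and that detail may properly sit in the SAP.

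What does not stand is the idea that the offset makes the model adequate. It depends on quantities that differ by outcome, and where it leaves the interval too wide, precision is given away.

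**Conclusion.** The mismatch between design and stated analysis is real and is written into Protocol 11.1. Its numerical effect is modest. Ignoring intervention-arm clustering makes the SE about 4% too small (two-sided error about 5.9%) at ICC 0.01 and 17 per cluster, or about 2.5% too small (5.6%) at 11 per cluster; both rest on the primary-outcome ICC carrying over. Omitting the stratification factors widens intervals by about 2.6% to 5.4% under an assumed 5% to 10% of residual variance. Net coverage may well be near 95%. It could be noticeably lower for an outcome with stronger clustering and little centre or stratum effect: about 91% at an assumed ICC of 0.05. The point is therefore one of aligning the model with the design and recovering precision. It does not show that the secondary results would be invalid.

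**What to change.** Amend Protocol 11.1 before data lock so that the model for continuous secondary outcomes contains arm, baseline value, IV-day stratum and centre. Add an arm-specific interventionist term for the intervention arm, or an equivalent variance estimate that allows for that clustering. With one interventionist per centre, this term is in effect a centre-by-arm random effect.

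Both parts should go in together. Centre main effects do not capture variation specific to one arm, and in the simulation centre and stratum alone gave 93.9% to 94.8% coverage. A therapist term limited to centres with several interventionists would leave most centres unmodelled. If the SAP already specifies a fuller model, the protocol wording should be brought into line with it.

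The cost is analysis work only: centre, IV days and baseline values are already collected. The limitation is that with at most 20 centres the interventionist variance may be poorly estimated, so the plan should say what is done if it is estimated at zero or the model does not converge.

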We have designed an intervention to help adult PWCF see how much treatment they use. We use dose-counting nebulisers to collect data and send it to a website, called CFHealthHub, where it can be displayed. We have worked with PWCF to make the information easy to understand. The website has modules which teach PWCF how to build successful treatment habits. We have developed a toolkit to help PWCF and a health professional (interventionist) work together to form habits of adherence to treatment. This trial will assess whether use of the CFHealthHub intervention, which includes the toolkit and website, reduces the amount of unscheduled emergency care PWCF require compared to those receiving standard care.

We will recruit PWCF for seven months at up to 20 CF units. We intend to recruit 556 PWCF overall. A computer will decide whether people who consent to be in the study will receive usual care alone or also receive the intervention. Both groups have a short period of two to four weeks when data is collected through their nebulisers and fed back to the website. It is only after that period that those allocated to the CFHealthHub group are allowed to use the website and receive enhanced care from the interventionist. After that point, all participants are followed up for 12 months. Participants will complete a series of questionnaires at the outset and at 12 months.

Quantitative data will be collected from the RCT CFHealthhub group, asking about acceptability of the intervention.

2. Introduction

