Figure 6. Participant timeline for the external pilot RCT Identification and approach, by letter, following up with phone call (pre-Consent form): 1) PWCF identified through the CF registry 2) Screened for eligibility (pre-screening tool): Inclusion: PWCF who have data within the CF registry aged > 16 years and taking inhaled mucolytics or antibiotics via a chipped nebuliser (e.g eTrack or I-Neb) or able and willing to take via eTrack or I-Neb. Exclusion: PWCF who are post-lung transplant or on the active lung transplant list, patients receiving palliative care, with palliative intent, for whom trial participation could be a burden, patients lacking in capacity to give informed consent or using dry Enrollment powder devices to take antibiotics or mucolytics. 3) Direct care team 1) Sends potential participant PIS and introductory letter by post and Interventionist follow's up by phone within 1 week to ensure they have received the information and allow an opportunity for questions AND/OR 2) Direct care team gives patients written information during routine clinic visit and asks permission to follow up the patient with a phone call to answer further questions and discuss involvement. CONSENT VISIT, at home or in clinic: 1) Screening form completed (confirmation of eligibility) 2) Informed consent 3) Data Collection: Intravenous days in last registry year; BMI; FEV1; EQ-5D-5L; PAM-13; CHAOS; MAD-3; SRBAI; CFQ-R; PHQ-8; GAD-7; COM-BMQ; Exacerbations form; subjective adherence question Participant given data logging nebuliser and Qualcomm hub. Randomisation (n~556): ACtiF interventionists randomises using web-based system between consent and baseline visits and informs participant ideally within 1 week of consent visit. Intervention arm Allocation Research: Monitoring and feedback (N=278): Initial Intervention visit: at home or in clinic (2-6 weeks from consent visit) (1 hour) 1) Adherence data uploaded, fed back and reasons for suboptimal adherence discussed in order to identify problems to solve using the Adherence Support Process; Control arm 2) Intervention chosen based on barrier from "library" in the Usual care n=278: Adherence Support Process; Adherence data uploaded. Care team and PWCF remain 3) Supportive contact offered via phone or email; and, blind to adherence data 4) Participants given personal access to CFHealthHub Manualised intervention delivered by trained researcher in initial intervention visit and subsequent visits normally every 4-6 weeks from this initial visit till six months visit (see below) ACtiF Researcher collects exacerbation data Data collected: Exacerbations form triggered by commencement of IV antibiotics; EQ5D-5L at both start and end of exacerbation episode Routine Clinic Visits: Data collected from all routine clinic visits after the date of consent. Follow-up Data collected by ACtiF researcher except where specified: (i) FEV1; (ii) subjective adherence question (iii) exacerbations form (iv) EQ5D-5L (v) Behavioural questionnaire. Adherence data continued to be uploaded to CFHealthHub Monthly follow up by CTRU researcher and/or ACtiF interventionist Monthly check of adherence data and contact with participant where missing adherence data or requirement to follow up on changes to prescription 12 month visit Primary clinical outcome: Number of exacerbations (Fuchs criteria) Secondary outcomes: BMI; FEV1; EQ-5D-5L; PAM-13; CHAOS; MAD-3; SRBAI; CFQ-r; PHQ-8; GAD-7; COM-BMQ; Exacerbations form; Other SAE's, resource use questionnaire

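### The adherence comparison is averaged from consent, so two to four (or six) weeks before the intervention starts count as outcome, and the use of baseline adherence is left unstated

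*Protocol*

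**What the plan says.** Section 11.1 fixes the adherence comparison in two statements. Mean adherence "between the CFHealthHub and control groups over the 12 month post-consent follow-up period will also be reported and compared between the groups". No covariate is named for this comparison, and its effect measure is described only in these terms: "a 95% confidence interval (CI) for the mean difference in this parameter between the randomised groups will also be calculated". In the same paragraph, an open-ended list of other continuous secondary outcomes "will be analysed with a multiple linear regression model with the baseline value of the outcome and randomised group as covariates".

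Section 6.4.4.1 hands out the chipped nebuliser and hub at the consent visit, so objective logging begins then. The lay summary describes two to four weeks of logging in both groups and adds: "It is only after that period that those allocated to the CFHealthHub group are allowed to use the website". Figure 6 places the initial intervention visit two to six weeks after consent.

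On disclosure, Figure 6 says that the interventionist randomises between the consent and baseline visits and "informs participant ideally within 1 week of consent visit". In section 9.3 the recruiting health professional is to "enter basic demographic information, after which the allocation will be revealed". Section 9.4 blinds only the statisticians.

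A baseline adherence level is presupposed elsewhere. Section 10.2.2 says "We will sample based on baseline adherence levels", and Table 3 marks objective adherence at the consent visit, which is the visit at which the device is first issued. Section 7.1.3 leaves further detail on the outcomes to the SAP.

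**The concern.** Adherence is the behaviour the intervention is meant to change, so this comparison will be used to interpret the primary result. During the run-in the intervention arm receives nothing that the control arm does not. Counting those weeks as outcome adds time in which no intervention effect is expected and moves the estimated difference towards zero.

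Those same weeks are the only trial-device adherence recorded before the intervention. They could serve as a baseline covariate, but section 11.1 assigns them to the outcome and does not say how baseline adherence will be used.

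The protocol also disagrees with itself about when the 12 months begin. An SAP that follows section 11.1 takes over the diluted window; one that follows the lay summary departs from section 11.1.

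**Working it through.** **The plan's own figure.** The protocol gives no target difference, SD or sample size for adherence. Its only sample size is for exacerbations (section 8.1.2: difference 0.5, SD 1.5, 90% power, two-sided 5%, ICC 0.01, cluster size 17, 20% loss), and it reproduces:

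- Design effect: 1 + 16 × 0.01 = 1.16.
- Per arm before clustering: 190 (normal) or 191 (t).
- 190 × 1.16 = 220.4, so 221; 191 × 1.16 = 221.6, so 222. The protocol states 222.
- 222 / 0.8 = 277.5, so 278 per arm and 556 in total, as stated.

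That calculation does not rest on adherence, so nothing below affects it.

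**Inputs for the dilution.**

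- Window: 12 months from consent, taken as 365 days (section 11.1).
- Time from consent to intervention: 2 to 4 weeks (lay summary) or 2 to 6 weeks (Figure 6).
- Assumptions: equal adherence in the arms during the run-in, a constant effect afterwards, each day weighted equally and, for power, an unchanged SD.

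**Formulas.** Pre-intervention share f = run-in days / 365. Estimated difference = (1 − f) × on-intervention difference. Sample size for equal power is multiplied by 1 / (1 − f)². Power for a comparison that would otherwise have 90% = Φ[(1.960 + 1.282)(1 − f) − 1.960].

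| Run-in | f | 10 points reads as | 20 points reads as | N multiplier | Power (from 90%) |
|---|---|---|---|---|---|
| 2 weeks | 14/365 = 3.8% | 9.6 | 19.2 | 1.08 | 87.6% |
| 4 weeks | 28/365 = 7.7% | 9.2 | 18.5 | 1.17 | 84.9% |
| 6 weeks | 42/365 = 11.5% | 8.8 | 17.7 | 1.28 | 81.8% |

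The 10-point and 20-point differences are illustrations. Section 6.4.1 cites an effect of up to 20% for personalised feedback; reading that as 20 points is an assumption. The power column is also illustrative, since adherence was not powered.

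**Baseline adjustment.** With correlation r between run-in and later adherence, the interval width is multiplied by √(1 − r²): 0.95, 0.87, 0.71 or 0.60 for r = 0.3, 0.5, 0.7 or 0.8. The protocol gives no r, so this range is assumed throughout.

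**Disclosure.** If participants are told at one week, 1 week of a two-week run-in, 3 of four or 5 of six are logged with the arm known.

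**Start of the 12 months, by place in the protocol.**

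- Lay summary: after the run-in.
- Section 6.4.4.6: final visit 12 months from consent.
- Section 7.1.1: post-baseline.
- Section 8.1.2: post-randomisation.
- Section 11.1: post-consent.

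**The case against.** The best defence is that a consent-anchored window is a reasonable choice. It matches the primary outcome window in section 11.1 and the final visit, gives both arms the same origin, and does not depend on whether or when an intervention visit took place. The bias is small, towards no difference, and on a secondary outcome; Appendix 1 lists no key secondary outcomes. The common origin is worth keeping, but a fixed later day in both arms keeps it too.

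The six-week bound comes only from Figure 6, which is captioned as the external pilot's timeline. It does carry main-trial content (about 556 participants, a 12-month visit), so it cannot be dismissed. On the lay summary alone the dilution stops at 7.7%. The intervention also works through gradual goal-setting and habit formation, so a constant effect is a simplification.

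Two stronger readings are tempting, and the document does not support them.

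- A reader might infer that the adherence comparison is raw or unadjusted. Section 11.1 does not say so. A mean difference can be a regression coefficient, the list of outcomes given the regression is open-ended, and section 7.1.3 leaves detail to the SAP. The protocol is silent on adjustment, and that is all that can be said.
- A reader might infer that participants learn their arm at the consent visit, so that disclosure must be delayed. Section 9.3 describes the allocation being revealed to the health professional; only Figure 6 covers telling the participant. Delaying disclosure would change trial conduct late in recruitment: first enrolment was anticipated for 11 September 2017 with seven months of recruitment, and this version is dated 12 February 2018, leaving about two months on plan.

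One caution stands against any use of the run-in as baseline. Part of it may follow disclosure, and section 10.1.1 concentrates data-transfer troubleshooting in the first two weeks, so early logs may be less complete.

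**Conclusion.** The point holds for the window. As written, section 11.1 counts pre-intervention time as adherence outcome and attenuates the difference by about 3.8% to 7.7%, and by up to 11.5% if the intervention starts at six weeks. This rests on no difference between arms in the run-in and a constant effect afterwards. If learning the allocation itself changes adherence, the first assumption fails and the attenuation could be smaller or larger. The conflict over when the 12 months start is plain on the face of the protocol.

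On adjustment, the conclusion is limited: the protocol does not state whether baseline adherence enters this comparison, although it states baseline adjustment for the listed continuous secondary outcomes. Adjusting would probably help precision, but the protocol gives no correlation from which to size the gain. The primary analysis and its sample size are unaffected. The change is still worth making, because adherence is the intervention's direct target and the remedy uses data already being collected.

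**What to change.** Amend section 11.1 and carry the wording into the SAP:

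1. Define baseline adherence as the first two weeks of logging in both arms.
2. Average the outcome from one fixed later day, the same in both arms, to 12 months. Anchor it to consent and not to the actual intervention visit, which control participants do not have. The choice of day decides what dilution remains. A start on day 15 leaves 14/351 = 4.0% if the intervention begins at four weeks and 28/351 = 8.0% at six. A start on day 29 leaves 0% and 14/337 = 4.2%.
3. Estimate the mean difference by regression on randomised group with baseline adherence, centre and IV-day stratum; the last two are the stratification factors in section 9.1.
4. Report the same comparison without baseline adherence as a sensitivity analysis, because Figure 6 lets part of the baseline period follow disclosure.
5. Reconcile the start of follow-up across the lay summary and sections 6.4.4.6, 7.1.1, 8.1.2 and 11.1, and the run-in length between the lay summary and Figure 6.

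The cost is analysis and protocol wording only. No new data, visits or change in the timing of disclosure are needed. The adherence window would no longer coincide exactly with the consent-anchored primary outcome window, and the report should say so.
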